### 16.2.1. DERIVATIONS

The following variables, as presented in the planned TLF shells, will be derived:

- Any time point:
  - o Per study vaccination and injection site reaction the worst case result is selected as the any timepoint assessment.
  - o Worst case assessment is defined as the largest measurement (mm) for assessments with measurements or the presence of the reaction if o measurements are available.
- Overall time point:
  - o Per injection site assessment the worst case result is selected as the overall assessment.
  - o Worst case assessment is defined as for the any timepoint assessment per study vaccination.

## 16.3. LABORATORY EVALUATIONS

The following tables are planned for presentation (based on the Safety analysis set for the Safety and Immunogenicity Cohort):

- Quantitative laboratory results and change from Baseline:
  - o Presented by means of default summary statistics for quantitative variables.
  - o Change from Baseline will be presented as well.
- Shift in laboratory grades from Baseline:
  - o Shift will be presented in terms of the number of participants with an increased toxicity grade from the Baseline result (refer to APPENDIX 7: Toxicity Grading Criteria):
    - 0 grades (no change in grade compared to Baseline or grade decreased).
    - 1 grade.
    - 2 grades.
    - 3 grades.
    - 4 grades (only applicable to certain tests).
  - o N1 is defined as the total number of participants with an assessment available at both Baseline and post-baseline time points.
  - o Due to the fact that the toxicity grading for Urine Erythrocytes is “Normal”, “Grade 1” or “Grade 2/3/4”, it is not possible to determine if there was an increase. Therefore Urine Erythrocytes will not be included in this table. The toxicity grading will be displayed in the listing.

The following listings are planned for presentation (based on the Randomized analysis set):

- Quantitative laboratory results.
- Qualitative laboratory results.
- Laboratory reference ranges by system and test (no analysis set applicable to this listing).

---

Document: Aeras\_C-040-404\_SAP\_V2\_0

Author: [name]

Version Number:

2.0

Version Date:

29SEP2017

Template No: CS\_TP\_BS016 – Revision 3

Reference: CS\_WI\_BS005

Effective Date: 01May2012

Copyright © 2012 Quintiles Transnational Corp. All rights reserved.

The contents of this document are confidential and proprietary to Quintiles Transnational Corp. Unauthorized use, disclosure or reproduction is strictly prohibited.

Refer to APPENDIX 5: Laboratory Assessments for a list of laboratory assessments.

The following laboratory variables, as presented in the planned TLF shells, will be collected during the study on the Hematology (HEMA), Chemistry (CHEM), Urinalysis (URIN), Pregnancy Test (PREG) and HIV Tests (HIVT) eCRFs:

- Date of sample collection.
- Time of sample collection (only applicable to pregnancy test results).
- Test.
- Reported results and unit.

All conversion of original to standard units will be completed by Data Management within the database prior to transfer to Biostatistics. All laboratory data will be summarized in the standard unit.

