Local BCG injection site reactions are well documented adverse events in subjects who receive BCG. Induration appears at the site of the BCG injection which is followed by a local lesion (redness and swelling) that may ulcerate some weeks later. In study C-013-404 all study participants received BCG at Study Day -42, before receiving AERAS-404 or placebo at Study Days 0, 56, and 231. Redness was the most common local BCG injection site reaction with all

subjects (100%) experiencing redness after BCG vaccination. Redness persisted in the majority of the subjects throughout the study, with at least 60% of subjects in each group having redness at the final study assessment. Swelling was the second most common local BCG injection site reaction. None of the redness or swelling at the BCG injection site met protocol-specified toxicity grading scale criteria for a severe (Grade 3 or higher) adverse event. BCG injection site ulceration occurred after BCG vaccination in both placebo and AERAS-404 recipients. There was no dose-related increase in frequency of BCG site ulceration after receiving AERAS-404. Overall, there was similar distribution of BCG local reactions in subjects who received AERAS-404 and placebo, with no dose response of BCG site reactions noted in subjects who received 2 doses or 3 doses of AERAS-404 and no evidence of acute worsening of BCG site reactions after AERAS-404 administration.

Table 1-2 presents the number and percentage of subjects in all four Phase 1 studies of AERAS-404 experiencing adverse events related to AERAS-404 for events occurring in  $\geq 5\%$  of subjects.

**Table 1-2 Adverse Events in the AERAS-404 Treatment Groups in Adults with Event Rate of  $\geq 5\%$  and Number of Subjects for Each Event**

Related Adverse Event a MedDRA Preferred Term b	AERAS-404 (N=198) c n d (%)
Injection site pain	109 ( 55.1)
Fatigue	95 ( 48.0)
Headache	82 ( 41.4)
Myalgia	76 ( 38.4)
Injection site swelling	39 ( 19.7)
Injection site erythema	37 ( 18.7)
Arthralgia	28 ( 14.1)
Pyrexia	25 ( 12.6)
Neutrophil count decreased	18 ( 9.1)
Application site hypersensitivity e	14 ( 7.1)
Chills	13 ( 6.6)
Diarrhoea	12 ( 6.1)
Protein urine	12 ( 6.1)
Red blood cells urine	12 ( 6.1)
Haemoglobin decreased	11 ( 5.6)
Nausea	10 ( 5.1)

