### 3.2.4 Exclusion Criteria

**Subjects must have none of the following at the time of randomization:**

1. Acute illness on Study Day 0
2. Axillary temperature  $\geq 37.5^{\circ}\text{C}$  on Study Day 0
3. Abnormal laboratory values from the most recent blood collected prior to randomization as follows:
  - Laboratory evidence of hematologic disease (white blood cell count  $< 3000/\text{mm}^3$  or  $> 11,500/\text{mm}^3$ ; hemoglobin  $< 0.9$  times the lower limit of normal of the testing laboratory, by age and gender; absolute neutrophil count  $< 1300/\text{mm}^3$ ; absolute lymphocyte count  $< 1000/\text{mm}^3$ )
  - ALT, AST, alkaline phosphatase, total bilirubin, creatinine, blood urea nitrogen (BUN)  $> 1.25$  times the upper limit of normal of the testing laboratory
4. Greater than Grade 1 on the Toxicity Scale urinalysis result (with the exception of hematuria in a menstruating female), or urinalysis abnormality judged clinically significant by the investigator
5. History or evidence of any clinically significant systemic disease, or any acute or chronic illness that might affect the safety, immunogenicity, or efficacy of study vaccine in the opinion of the investigator
6. History of treatment for active TB disease or latent *Mtb* infection
7. History or evidence, including chest X-ray, of active TB disease
8. Shared residence with an individual receiving anti-TB treatment, or known to have incompletely treated culture or smear positive TB, at screening
9. History of autoimmune disease or immunosuppression
10. Used immunosuppressive medication within 42 days before Study Day 0 (inhaled and topical corticosteroids are permitted)
11. Received immunoglobulin or blood products within 42 days before Study Day 0

12. Received any investigational drug therapy or investigational vaccine within 182 days before Study Day 0, or planned participation in any other clinical trial during the study period
13. Received investigational TB vaccine, other than BCG, at any time prior to Study Day 0
14. Planned administration/administration of a licensed vaccine in the period starting 28 days before and ending 28 days after each dose of study vaccine
15. History or laboratory evidence of any past or present possible immunodeficiency state including, but not limited to, any laboratory indication of HIV-1 infection
16. History of allergic disease or reactions, including eczema, likely to be exacerbated by any component of the study vaccine

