##### **Abnormal Clinical Assessments and Laboratory Tests**

Results from clinical laboratory tests obtained on the study must be promptly reviewed by the investigator (or a designee who is a medically qualified study team member) as per site policy to determine if abnormalities exist. If the laboratory value is abnormal and has increased in toxicity grade (see Appendix C for toxicity grading scales) from pre-vaccination values, it must be reported as an adverse event and repeated promptly at the investigator's discretion to demonstrate resolution. Additional laboratory tests may be performed if the investigator deems them to be necessary to fully evaluate an adverse event. In the event that the investigator elects to order non-protocol-specified laboratory tests, the investigator must record the rationale for the tests and a determination of clinical significance of the result in the source documents. The investigator must keep the medical monitor informed of adverse events of clinical significance.

Abnormal results and findings will be discussed with the subject, and the subject will be referred for follow-up with their healthcare provider if necessary.

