### 2.1. PRIMARY OBJECTIVES

The primary objectives are:

- To evaluate the safety profile in human immunodeficiency virus (HIV)-uninfected, remotely Bacillus Calmette-Guérin (BCG) vaccinated adolescents of:
  - o H4:IC31 (also known as AERAS-404).
  - o BCG revaccination.
- To evaluate prevention of *Mycobacterium tuberculosis* (*Mtb*) infection, as measured by rates of conversion using a QuantiFERON Tuberculosis (TB) gold-in-tube (QFT-GIT) assay of:
  - o H4:IC31 compared to Placebo.
  - o BCG revaccination compared to Placebo.

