- On 5 April 2016, Aeras Biostatistics and Data Management were notified of a manufacturer's recall of a portion of the QuantiFERON (QFT) tubes that were used in determination of endpoints. The recall primarily stemmed from changes in Qiagen's quality control (QC) process, which resulted in their recalling all unexpired partial lots that had been previously circulated for use. Although Qiagen's ongoing QC processes did not detect a spike in false positive results within this partial lot, they were unable to rule out the possibility of false positive results coming from the tubes in question, thereby resulting in the recall.
  - o Sixteen (16) positive QFT results came from these recalled tubes, affecting 14 unique participants. Nine (9) of the tubes contributed toward the trial's primary efficacy endpoint. Even though the information provided by Qiagen does not suggest that these results are false positives, the tubes were recalled nonetheless. Therefore, in an abundance of caution, Aeras considered an additional analysis set that would remove these results from the primary endpoint and final endpoint analysis.

Aeras requested the following approach to handle this:

- o Create an additional analysis set (refer to Section 5.4: Adjusted Modified Intent-to-treat (first recall positive omit Analysis Set)).
- o Perform the following additional analysis:
  - Modified Intent-to-treat (mITT) with adjudication: This analysis will retain QFT data from all visits for participants who received positive QFT results from recalled tubes provided they also received positive results from non-recalled tubes. In other words, if a participant has positive QFT results from both non-recalled and recalled tubes, then all of these results will be treated as true positives.
- Whilst setting up the programming for the medical review listings, Data Management (DM) was requested to use the following toxicity criteria for Urine Erythrocytes since this is recorded as a qualitative value and the protocol provides the toxicity criteria for quantitative values. These criteria will be used to determine the toxicity grading. ++/+++ values will therefore be regarded as 'Grade 2/3/4'.

Laboratory Test	Grade 1	Grade 2	Grade 3	Grade 4
Urine Erythrocytes	+	++/+++	++/+++	++/+++

Document: Aeras\_C-040-404\_SAP\_V2\_0

Author: [name]

Version Number:

2.0

Version Date:

29SEP2017

Template No: CS\_TP\_BS016 – Revision 3

Reference: CS\_WI\_BS005

Effective Date: 01May2012

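### SAP 16.3 drops urine erythrocytes from the shift-in-grade table for a reason its own grading contradicts: an increase can be determined in 8 of 9 transitions

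*SAP*

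**What the plan says.** Safety is a primary objective. SAP 2.1 reads "To evaluate the safety profile in human immunodeficiency virus (HIV)-uninfected, remotely Bacillus Calmette-Guérin (BCG) vaccinated adolescents of" H4:IC31 (AERAS-404) and BCG revaccination.

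SAP 16.3 plans two laboratory tables, both restricted to the Safety and Immunogenicity Cohort (30 planned per arm). One summarises quantitative results and change from Baseline. The other, the shift table, counts participants whose toxicity grade rose from Baseline by 0, 1, 2, 3 or 4 grades. It is the only laboratory table in that section that uses grades.

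Urine erythrocytes are recorded qualitatively. SAP 3.3 and Appendix 7 make + Grade 1, and SAP 3.3 says that ++/+++ "values will therefore be regarded as" a combined Grade 2/3/4. SAP 16.3 then states that "it is not possible to determine if there was an increase. Therefore Urine Erythrocytes will not be included in this table"; the grading is to be shown in a listing. SAP 16.3.1 adds that, for some tests, Grades 3 and 4 rest on clinical judgment and are not assigned for analysis.

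Protocol 7.5.1 calls for the number and percentage of participants with newly abnormal laboratory values of Grade 1 or above, at each post-vaccination time point and overall.

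Protocol Table 1-2 covers adults "experiencing adverse events related to AERAS-404 for events occurring in" at least 5% of subjects. It includes "Red blood cells urine" (12 of 198) and "Neutrophil count decreased" (18 of 198). Neutrophils are measured in this trial but have no row in the toxicity table of Protocol Appendix B or SAP Appendix 7, and SAP Appendix 5 shows a dash for them.

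**The concern.** The stated reason confuses two questions: whether a grade rose, and by how many grades. Collapsing Grades 2 to 4 blurs the second. It leaves the first almost untouched, because the three remaining categories are still ordered.

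The test removed corresponds to a laboratory finding already judged related to the vaccine in adults, and this is the vaccine's first use in adolescents. The Protocol 7.5.1 tabulation could have covered the gap, since + and ++/+++ are both at least Grade 1. No such table is visible in SAP 16.3, and the text of SAP 3.3 available for this review does not list its removal. At stake is a systematic count by arm of new or worsened urine red cells, taken from the scheduled tests themselves and not dependent on what is reported as an adverse event.

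**Working it through.** **Inputs.** Categories and grades: SAP 3.3, 16.3 and Appendix 7. Eligibility: Protocol 3.2.4, exclusion criterion 4. Earlier rates: Protocol Table 1-2, N = 198. Cohort size: SAP Table 1, 30 per arm.

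**Step 1. The protocol's own rates.** 12/198 = 6.06%, printed as 6.1%. 18/198 = 9.09%, printed as 9.1%. Both reproduce.

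**Step 2. The nine transitions.** Let Normal be grade 0, + be grade 1, and ++/+++ be any of grades 2, 3 or 4. As in SAP 16.3, decreases count as 0 grades.

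| Baseline | Follow-up Normal | Follow-up + | Follow-up ++/+++ |
|---|---|---|---|
| Normal | no increase | increase, 1 grade | increase, 2 to 4 grades |
| + | no increase | no increase | increase, 1 to 3 grades |
| ++/+++ | no increase | no increase | undetermined, 0 to 2 grades |

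Whether there was an increase is settled in 8 of 9 cells. The exact number of grades is settled in 6 of 9.

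**Step 3. How reachable is the ambiguous cell?** It needs a Baseline of ++/+++, that is, above Grade 1. Exclusion criterion 4 bars urinalysis results above Grade 1 at entry, except haematuria in a menstruating female. Apart from eligibility deviations, the cell is confined to that exception.

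**Step 4. The alternative reading of ++/+++.** If the rule in SAP 16.3.1 on clinical-judgment grades covers haematuria, ++/+++ would be assigned Grade 2. The grades would then be 0, 1 and 2, and both the presence and the size of an increase would be settled in all 9 cells. SAP 3.3, 16.3 and 16.3.1 do not say the same thing about this result.

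**Step 5. Scale, for illustration only.** Assume the pooled adult rates carried over to 30 H4:IC31 recipients. Urine red cells: 30 × 12/198 = 1.8 expected participants. Low neutrophils: 30 × 18/198 = 2.7. At half those rates the figures are 30 × 6/198 = 0.9 and 30 × 9/198 = 1.4. The documents do not establish that any of these rates apply here.

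**The case against.** The strongest reply is that the table's rows are numbers of grades, and a move into Grade 2/3/4 has no single size. That is true for two of the nine cells, in addition to the ambiguous one. It justifies a different layout for this test, but not its removal.

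The second reply is that the shift table is not the main safety result. Protocol 7.5.1 makes adverse events the primary safety variable and says laboratory abnormalities will also be reported as adverse events. Protocol 3.6.3.2 requires such a report "If the laboratory value is abnormal and has increased in toxicity grade" from the pre-vaccination value, so a move from Normal to + qualifies. SAP 16.1.2 tabulates adverse events by term, severity and relationship, and the grades are listed. All of this stands. A reader might infer that haematuria could not show up in any comparison with placebo, or that the shift table would give false reassurance. The documents do not support either: the adverse event route is open, and the SAP states the omission openly.

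For neutrophils, a reader might infer a SAP error or a signal that goes unreported. Neither follows. The SAP copies the protocol's toxicity table faithfully. Protocol 5.3 counts changes in laboratory safety parameters as adverse events even without a grade, and Protocol 5.4 lets severity be judged for events outside the table. Neutrophils are also in the planned change-from-Baseline summary, which under SAP 6.4 shows the minimum. What is absent is an automatic grade-based trigger and a count of participants who became abnormal.

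Finally, Table 1-2 pools adults across doses and regimens, including some given H4 alone, and has no placebo column. It makes the finding worth tabulating; it does not predict this trial's counts.

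**Conclusion.** The stated reason for dropping urine erythrocytes is incorrect: an increase is determinable in 8 of 9 transitions, and eligibility largely closes off the ninth. The consequence is limited. The systematic by-arm laboratory comparison omits one test, while the adverse event tables and a listing can still carry the finding. The count of 8 rests only on the SAP's own ordered categories. The expected counts rest on an untested carry-over of adult rates and are illustrative.

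The absence of the Protocol 7.5.1 tabulation is judged on the visible SAP text; the table shells mentioned in SAP 8 were not available. The neutrophil point is a reasonable optional addition and not a defect of the SAP. The correction is worth making because it serves a primary objective at almost no cost.

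**What to change.** 1. In SAP 16.3, keep urine erythrocytes as a three-category shift (Normal, +, ++/+++) and give the number of participants with any increase by arm and visit. Alternatively, add the Protocol 7.5.1 count of participants newly abnormal at Grade 1 or above, by time point and overall. Note menstruation where it was recorded. The Day 63 column applies only to H4:IC31 and placebo, since BCG recipients have post-vaccination urinalysis at Day 7 only.
2. Reconcile SAP 3.3, 16.3 and 16.3.1 on how ++/+++ is graded for analysis, and correct the sentence saying that an increase cannot be determined.
3. Optional: beside the planned change-from-Baseline summary, add a descriptive count by arm and visit of participants with neutrophils newly below the laboratory's lower limit. Any toxicity cut-off is for the sponsor to choose.

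The cost is a wording change and a few extra rows from data already collected. The downside is that somewhat more laboratory shifts will be reported, some of them menstrual.

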### 16.3.1. TOXICITY GRADING CRITERIA

The toxicity grades will be assigned based on the protocol-specific criteria specified in APPENDIX 7: Toxicity Grading Criteria. For some assessments grade 3 or 4 cannot be assigned programmatically, but rather are based on clinical judgment, therefore they are not assigned for the purpose of analysis.

Refer to APPENDIX 5: Laboratory Assessments for a list of tests for which toxicity grades will be programmatically assigned.

## 16.4. VITAL SIGNS

Vital signs will be presented for the Safety analysis set.

The following tables are planned for presentation:

- Vital signs and change from pre-vaccination:
  - o Presented by means of default summary statistics for quantitative variables.
  - o Change from pre-vaccination will be presented as well.
- Shift in vital signs toxicity grades from pre-vaccination (Study Day 0 or Study Day 56 [not applicable to BCG]):
  - o Shift will be presented in terms of the number of participants with an increased toxicity grade from the pre-vaccination results (refer to):
    - 0 grades (no change in grade compared to Baseline or grade decreased).
    - 1 grade.
    - 2 grades.
    - 3 grades.
  - o N1 is defined as the total number of participants with an assessment available at both the relevant pre- and post-vaccination time points who received the applicable study vaccine dose.

---

Document: Aeras\_C-040-404\_SAP\_V2\_0  
Author: [name]

Version Number: 2.0  
Version Date: 29SEP2017

Template No: CS\_TP\_BS016 – Revision 3  
Effective Date: 01May2012

Reference: CS\_WI\_BS005

The following listing is planned for presentation (based on the Randomized analysis set):

- Vital signs results.

The following vital signs variables, as presented in the planned TLF shells, will be collected on the Vital Signs, Vital Signs - Pre-vaccination and Vital Signs - Post-vaccination eCRFs:

- Result and unit for each of the following test:
  - o Axillary temperature (°C).
  - o Pulse rate (beats per minute).
  - o Systolic and diastolic blood pressure (mmHg).

#### 16.4.1. TOXICITY GRADING CRITERIA

The toxicity grades will be assigned based on the protocol-specific criteria specified in APPENDIX 7: Toxicity Grading Criteria. Grade 4 cannot be assigned programmatically but rather is based on clinical judgment, therefore not assigned for the purpose of analysis.

Refer to APPENDIX 6: Vital Signs Assessments for a list of tests for which toxicity grades will be programmatically assigned.

#### 16.4.2. PRE-VACCINATION AND POST-VACCINATION TIME POINTS

Refer to Table 4: Vital Signs Pre-and Post-vaccination Time Points below for details on the relevant pre-and post-vaccination time point for the vital signs assessments.

Study Vaccination	Pre-vaccination Time Point	Post-vaccination Time Point
Dose 1	Study Day 0 (Pre-vaccination)	Study Day 0 (Post-vaccination)
Dose 2 (not applicable to BCG)	Study Day 56 (Pre-vaccination)	Study Day 56 (Post-vaccination)

### 16.5. PHYSICAL EXAMINATION

Physical examination data will be presented for the Randomized analysis set.

The following listing is planned for presentation:

- Abnormal physical examination findings:
  - o Only include physical examination results where the result is indicated as abnormal.

The following physical examination variable, as presented in the planned TLF shells, will be collected on the Physical Examination eCRF:

- Date of assessment.
- Verbatim term (and abnormality description if applicable).

Document: Aeras\_C-040-404\_SAP\_V2\_0

Author: [name]

Version Number:

2.0

Version Date:

29SEP2017

Template No: CS\_TP\_BS016 – Revision 3

Reference: CS\_WI\_BS005

Effective Date: 01May2012

Copyright © 2012 Quintiles Transnational Corp. All rights reserved.

The contents of this document are confidential and proprietary to Quintiles Transnational Corp. Unauthorized use, disclosure or reproduction is strictly prohibited.

